7.3.4.2.3 Pregnancy

A female subject must be instructed to stop taking the test “drug” and immediately inform the investigator if she becomes pregnant during the study. The investigator should counsel the subject; discuss the risks of continuing with the pregnancy and the possible effects on the foetus. Monitoring of the patient should continue until conclusion of the pregnancy. Pregnancies occurring up to 90 days after the completion of the study medication must also be reported to the investigator.

Pregnancy occurring in the partner of a male subject participating in the study should be reported to the investigator and the Sponsor. The partner should be counselled, the risks of continuing the pregnancy discussed, as well as the possible effects on the foetus. Monitoring of the patient should continue until conclusion of the pregnancy.

NOTE: The Investigator should fill out a *Pregnancy Reporting Form* only if the pregnant partner has signed a Pregnant Partner Data Release Form.

In the event that the EDC system is unavailable, the Clinical Trial Pregnancy Reporting Form provided to investigators should be completed and submitted to the Sponsor or its designee immediately (i.e., no more than 24 hours after learning of the pregnancy), either by faxing or by scanning and emailing the form using the fax number or email address provided to investigators. Once the EDC system is available, all information will need to be entered and submitted via the EDC system.

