3. STUDY DESIGN

3.1 OVERVIEW OF STUDY DESIGN

[figure not shown]
This is an open-label, multicentre, multinational, phase II study exploring the efficacy and safety of vemurafenib in a diverse population of patients with cancers (excluding melanoma and papillary thyroid cancer) known to harbour BRAF V600 mutations and for whom vemurafenib is deemed the best treatment option in the opinion of the Investigator.

In the population of colorectal cancer patients, the safety and efficacy of vemurafenib in combination with cetuximab will also be explored in addition to vemurafenib monotherapy.

Patients with BRAF V600 mutation-positive cancers will be identified through mutation analysis assays as routinely performed at each participating site according to their local procedure. The BRAF V600 mutation identified at the site, as well as the specific BRAF mutation assay that was performed, will be recorded in the electronic case report form (eCRF). The presence of BRAF V600 mutations will be retrospectively confirmed by the Roche CoDx cobas 4800 BRAF V600 Test or other standard methodology.

The trial will consist of a Screening Period (Day -28 to -1), a Treatment Period, an End of Treatment Visit occurring when study medication is discontinued for any reason, a Safety Follow-Up Visit occurring 28 days (\pm 5 days) after the last dose of study medication and a Survival Follow-Up Period lasting for a minimum of 12 months after the last patient has been enrolled or until all patients have died, withdrawn consent or are lost to follow-up (whichever occurs first) to monitor survival status. Day 1 of the study (baseline) will be defined as the first day a patient receives study medication. One cycle of therapy will be defined as 28 days of treatment. Patients will be asked to attend clinic visits at regular intervals during the study for safety and efficacy assessments.

Figure 1: Study Design

The study will include 7 cohorts of patients with the following cancers:

- Cohort 1: Non-small cell lung cancer (NSCLC)
- Cohort 2: Ovarian cancer
- Cohort 3: Colorectal cancer
 - Cohort 3a: Vemurafenib only
 - Cohort 3b: Combination therapy with vemurafenib and cetuximab
- Cohort 4: Cholangiocarcinoma / cancer of the biliary tract
- Cohort 5: Breast cancer
- Cohort 6: Multiple myeloma (MM)
- Cohort 7: Solid tumours other than the above

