16. Fertile men and women must use an effective method of contraception during treatment and for at least 6 months after completion of treatment as directed by their physician. Effective methods of contraception are defined as those which result in a low failure rate (i.e., less than 1% per year) when used consistently and correctly (for example implants, injectables, combined oral contraception or intra-uterine devices). At the discretion of the Investigator, acceptable methods of contraception may include total abstinence in cases where the lifestyle of the patient ensures compliance. (Periodic abstinence [e.g., calendar, ovulation, symptothermal, postovulation methods] and withdrawal are not acceptable methods of contraception).
17. Absence of any psychological, familial, sociological, or geographical conditions potentially hampering compliance with the study protocol and follow-up schedule; those conditions should be discussed with the patient before trial entry

*For prostate cancer, ECD and/or LCH specific eligibility criteria as part of Cohort 7, see [Appendix 9](#) and [Appendix 10](#), respectively.

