7.3.4 Immediate Reporting Requirements from Investigator to Sponsor

Certain events require immediate reporting to allow the Sponsor to take appropriate measures to address potential new risks in a clinical trial. The investigator must report such events to the Sponsor immediately; under no circumstances should reporting take place more than 24 hours after the investigator learns of the event. The following is a list of events that the investigator must report to the Sponsor within 24 hours after learning of the event, regardless of relationship to study drug:

- Serious adverse events (see [Section 7.3.4.1](#) for further details)
- Non-serious adverse events of special interest (see [Section 7.3.4.2](#) for further details)
- Pregnancies (see [Section 7.3.4.2.3](#) for further details)

The investigator must report new significant follow-up information for these events to the Sponsor immediately (i.e., no more than 24 hours after becoming aware of the information). New significant information includes the following:

- New signs or symptoms or a change in the diagnosis
- Significant new diagnostic test results
- Change in causality based on new information
- Change in the event's outcome, including recovery
- Additional narrative information on the clinical course of the event

Investigators must also comply with local requirements for reporting SAEs to the local health authority and IRB/EC.

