7.3.4.2 Reporting of Protocol-Defined Events of Special Interest

7.3.4.2.1 Abortion, Congenital Anomaly, and Birth Defects

Abortions, congenital anomalies, and birth defects are events of special interest and will need to be reported to the Sponsor expeditiously.

Abortion, whether accidental, therapeutic, or spontaneous, should always be classified as serious (as the Sponsor considers these medically significant), recorded on an SAE eCRF page, and expeditiously reported to the Sponsor.

Any congenital anomaly/birth defect in a child born to a female patient or female partner of a male patient exposed to the investigational product should be recorded and reported as an SAE.

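### The explicit post-treatment pregnancy reporting duty stops at 90 days, while the protocol requires contraception for at least 6 months

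*Protocol*

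**What the plan says.** Criterion 16 in Section 4.2, repeated in the Synopsis, sets the contraception period: "Fertile men and women must use an effective method of contraception during treatment and for at least 6 months after completion of treatment".

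Section 7.3.4.2.3 deals with pregnancies in three places:

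- A female subject must stop the drug and "immediately inform the investigator if she becomes pregnant during the study". Counselling and monitoring to the end of the pregnancy follow from this.
- The post-treatment limit is: "Pregnancies occurring up to 90 days after the completion of the study medication must also be reported to the investigator".
- For partners: "Pregnancy occurring in the partner of a male subject participating in the study should be reported to the investigator and the Sponsor". No post-treatment window is given. The reporting form is to be completed "only if the pregnant partner has signed a Pregnant Partner Data Release Form".

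Section 7.3.4 lists pregnancies among the events that go to the Sponsor within 24 hours of the investigator learning of them. It states no window and refers back to Section 7.3.4.2.3.

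**The concern.** The sponsor has chosen 6 months as the time after treatment in which pregnancy should be avoided. The only numbered limit on post-treatment pregnancy reporting falls halfway through that time, and the protocol gives no reason for the difference. If contraception fails in the second half of the period, sites can reasonably read the text in different ways: one would report, counsel and follow the pregnancy, another would not. What is at stake is consistent safety follow-up of a small number of pregnancies. The documents give no count of expected cases, and none is assumed here.

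**Working it through.** The plan has no figure of its own to reproduce on this point. The check is a comparison of two windows, a search for any other clause that covers the difference, and a look at residual exposure.

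**Step 1: the difference between the windows.** Inputs: at least 6 months (criterion 16) and 90 days (Section 7.3.4.2.3), both counted from completion of treatment. Six months is about 182 days.

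182 − 90 = 92 days, that is about days 91 to 182.

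This is calendar time, not a measure of risk.

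**Step 2: does another clause cover days 91 to 182?**

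- *Female-subject sentence (7.3.4.2.3).* It applies during the study. Section 3.1 counts as part of the trial "a Survival Follow-Up Period lasting for a minimum of 12 months after the last patient has been enrolled", so the phrase can reach past day 90. The same sentence tells her to stop the drug, which suggests the treatment period. The 90-day sentence is also worded as an addition, and it would be largely redundant if survival follow-up were already covered. Both readings are tenable.
- *Partner paragraph (7.3.4.2.3).* It is tied to the male subject taking part in the study and has no window. The 90-day sentence does not say whose pregnancies it means, so partners may be capped at 90 days or not capped at all.
- *24-hour list (7.3.4).* It has no window of its own and points back to 7.3.4.2.3.
- *General event reporting (7.3.1).* Serious events and events of special interest are reported until 28 days after the last dose. After that, only serious events believed to be drug-related need be notified, and only if the investigator becomes aware of them.
- *Outcome route (7.3.4.2.1).* "Abortion, whether accidental, therapeutic, or spontaneous, should always be classified as serious". Birth defects are also reportable, and this section states no time limit. It covers certain outcomes, not the pregnancy itself or its follow-up.

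No clause states a duty for days 91 to 182, and none excludes one.

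**Step 3: residual vemurafenib at day 90.** Section 1.3.3 gives an apparent mean half-life of about 90 hours, with a range of 30 to 145 hours. First-order elimination is assumed.

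- Day 90 = 90 × 24 = 2160 hours.
- At the mean: 2160 / 90 = 24.0 half-lives.
- At the longest: 2160 / 145 = 14.9 half-lives, and 2^−14.9 ≈ 0.000033, about 0.003% remaining.

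The protocol gives no half-life for cetuximab, so nothing is concluded about exposure to that drug in Cohort 3b.

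**The case against.** The strongest reply is that there is no contradiction. Contraception is a precaution asked of the patient and the 90-day rule is a reporting duty; both can be met, and nothing requires them to be equal. On the exposure figures above, 90 days is a defensible limit for vemurafenib. Moreover, the trial by its own description includes survival follow-up, the 24-hour duty to the Sponsor depends on when the investigator learns of the pregnancy, and no text tells a site to withhold a later report.

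Much of this stands. A reader might infer that pregnancies from day 91 onward are excluded from reporting, or that they will go unreported. The documents do not support that: the female-subject sentence and the partner paragraph can each be read to include them. Nor do the documents support the inference that these pregnancies carry meaningful vemurafenib exposure.

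The reply does not remove the mismatch. The one explicit limit ends inside the period the sponsor itself set for avoiding pregnancy, without explanation, and coverage of the remainder depends on how a site reads an undefined phrase.

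**Conclusion.** The point holds as a minor inconsistency in safety reporting. About 92 days of the required contraception period have no explicit duty of pregnancy reporting, counselling or follow-up, and whether other wording covers them is unclear. The 92 days rest on taking 6 months as about 182 days. Because criterion 16 says at least 6 months, the difference would be larger wherever a longer period is advised.

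The gain from a change is small: vemurafenib exposure by then is negligible, some cases may already be covered, and some outcomes have their own route. No endpoint, sample size, error rate or analysis is affected. It is a cheap improvement, not a flaw that threatens the trial.

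**What to change.** In Section 7.3.4.2.3, replace the 90-day limit with 6 months after the last dose of study medication. Add that this applies to female patients and to partners of male patients, with partner data still subject to the existing release form.

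Optionally, remind patients of this duty at safety assessments that already exist: the 28-day Safety Follow-Up Visit, and the assessments 6 months after discontinuation or before another anti-neoplastic therapy (Synopsis, Length of Study; Section 5.3.4). No new visit and no pregnancy questioning beyond those assessments is needed.

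The cost is one amended sentence with its clarification, and perhaps a few more pregnancy reports. As a protocol modification it goes to the ethics committees under Section 12, and it can be carried in the next amendment.

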7.4 WARNINGS AND PRECAUTIONS

No evidence available at the time of the approval of this study protocol indicated that special warnings or precautions were appropriate, other than those noted in the vemurafenib IB and described in this Protocol.

8. STATISTICAL CONSIDERATIONS AND ANALYTICAL PLAN

8.1 PRIMARY AND SECONDARY STUDY VARIABLES

8.1.1 Primary Variable

Response rate at Week 8, as assessed by the Investigator using RECIST, v1.1* for patients with solid tumours or IMWG uniform response criteria for patients with MM, is the primary endpoint for each cohort. For patients with solid tumours, responders at Week 8 will be defined based on tumour assessment status of PR or CR at Week 8. For patients with MM, responders at Week 8 will be defined based on tumour assessment status of CR, sCR, VGPR or PR. Only patients with measurable disease at baseline will be included in the analysis of the RR. Patients without a post-baseline tumour assessment will be considered to be non-responders.

There will be 7 cohorts with different cancer types. There will be Cohort 3a and 3b with patients with colorectal cancer treated with vemurafenib or vemurafenib in combination with cetuximab, respectively.

Cohort 3b has two parts,

Part 1 is a dose finding phase for vemurafenib in combination with cetuximab (based on a classical 3+3 design)

Part 2 is investigating the efficacy and safety of the recommended dose for stage I/II of the combination of vemurafenib and cetuximab

*see [Appendix 9](#) for prostate cancer, [Appendix 10](#) for ECD and/or LCH response criteria

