Efficacy of vemurafenib for solid tumours and MM and vemurafenib in combination with cetuximab in colorectal cancer will be captured by Response Rate (RR), clinical benefit rate (CR or sCR, PR or VGPR and stable disease [SD]), and time-dependent endpoints (DOR), overall response rate assessed via best overall response (BOR), time to response, time to tumour progression, PFS and OS).

The primary endpoint will be RR at Week 8 in each indication. For solid tumours to be assigned a status of partial response (PR) or complete response (CR) (i.e., a responder), changes in tumour measurements must be confirmed by repeat assessments performed no less than 4 weeks after the criteria for response are first met, i.e., patients need to have two consecutive assessments of PR or CR to be responders.

For patients with solid tumours, response will be assessed according to RECIST, v1.1, criteria (Eisenhauer EA et al. Eur J Cancer 2009;45(2):228-47). Assessments will be performed by the Investigator using computed tomography (CT) or magnetic resonance imaging (MRI) scan every 8 weeks (see [Appendix 4](#)).

For prostate cancer, ECD and or LCH specific response criteria see [Appendix 9](#) and [Appendix 10](#), respectively.

For patients with MM, response will be assessed according to International Myeloma Working Group [IMWG] uniform response criteria (Durie BGM et al. Leukemia 2006;20:1467-73.), e.g., patients need to have two consecutive assessments of CR, sCR, VGPR or PR to be responders. Assessments will be performed by the Investigator 8 weeks after starting vemurafenib and every 28 days thereafter. Bone marrow assessments will be performed only once to confirm CR or sCR.

Secondary endpoints for solid tumours and MM will include duration of response (DOR), time to response, time to progression (TTP), overall response rate (ORR), clinical benefit rate (CR or sCR, PR or VGPR and stable disease [SD]), time to tumour progression, PFS, and overall survival (OS).

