The analysis at Stage II (for lower or higher desirable confirmed response) for each cohort will be performed when all patients enrolled in the study, as estimated in the Sample Size section, will have a minimum of 8 weeks of treatment, develop progressive disease, withdraw, or are lost to follow-up, whichever occurs first.

In case a cohort/indication is expanded up to 70 patients, the primary analysis for efficacy will occur once all patients have been followed up for 9 months after last patient had been enrolled in that cohort, or the patient develops progressive disease, withdraws consent, or is lost to follow-up, whichever occurs first.

Secondary efficacy variables (final analysis)

The final analysis for each cohort will take place when all patients in that cohort have been followed for survival for a minimum of 12 months after the last patient has been enrolled or until all patients have died, withdrawn consent or are lost to follow up, whichever occurs first. More details are in Efficacy Analysis Data ([Section 8.3.2](#)).

Hypothesis Testing

The adaptive two-stage design allows the original estimation of the Stage II response rate to be reassessed, based on information at Stage I, in the event that it was too optimistic or too sceptical to be the true response rate.

For example, for patients in each cohort, we assume that RR of 15% would be a very low RR and vemurafenib will be “under-performing” for this cohort. A RR of 45% would be a high desirable RR, while a RR of 35% would be a low desirable RR, for Stage II.

The hypotheses for all cohorts for Stage I are:

- a. $H_0: \pi_{N1} < \pi_0$ where $\pi_0 = 15\%$
- b. $H_1: \pi_{N1} \geq \pi_0$ where $\pi_0 = 15\%$

where N_1 is a number of patients in Stage I and π_0 is a very low, undesirable RR.

If H_0 is rejected (and H_1 is accepted at Stage I), further patients will be enrolled based on the number of responders in Stage I and their data will be collected in the second stage.

The hypotheses for all cohorts at the end of Stage II for a low desirable response, π_{1L} , are:

- i) H_1 is accepted at Stage I and

- ii) $H_0: \pi_N \leq \pi_{1L}$ where $\pi_{1L} = 35\%$
- $H_1: \pi_N > \pi_{1L}$ where $\pi_{1L} = 35\%$

The N notifies the total number of patients for each cohort.

The hypotheses for all cohorts at the end of Stage II for a high desirable response, π_{1H} , are:

- i) H_1 is accepted at Stage I and
- ii) $H_0: \pi_N \leq \pi_{1H}$ where $\pi_{1H} = 45\%$

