5.3.6 Response Criteria

5.3.6.1 Solid tumours

Response of measurable solid tumours to study treatment will be evaluated by the Investigator according to RECIST, v1.1 criteria ([Appendix 4](#)) (67). See [Appendix 9](#) for prostate, [Appendix 10](#) for ECD and/or LCH specific response criteria.

Tumour evaluations will occur once during the Screening Period (Days –28 and –1), every 8 weeks after starting vemurafenib during the Treatment Period, and at the End of Treatment Visit. A window of \pm 5 days of scheduled visit is allowed to complete the tumour assessments at the required intervals.

Radiological tumour assessments to measure extent of disease will be carried out by CT/MRI of the chest/abdomen/pelvis (C/A/P) for all patients. In addition, CT/MRI of the brain can be performed if clinically indicated and as per standard care.

Patients should be assessed at the designated time points using a consistent imaging modality. The same imaging technique must be used for a patient throughout the study. The same method of assessment and the same technique should be used to characterize each identified and reported lesion at baseline and during follow-up. If more than one method of assessment is used at baseline, the most accurate method according to RECIST should be selected when recording data; in addition, this method should be performed in all subsequent evaluations. Tumour measurements should be made by the same Investigator/radiologist for each patient during the study to the extent that this is feasible.

For solid tumours to be assigned a status of partial response (PR) or complete response (CR) (i.e., a responder), changes in tumour measurements must be confirmed by repeat assessments performed no less than 4 weeks after the criteria for response are first met, i.e., patients need to have two consecutive assessments of PR or CR to be a responder.

Symptomatic deterioration may indicate progressive disease (PD). However, radiological confirmation of PD is strongly recommended.

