5.3.6.2 Multiple myeloma

Response of MM to study treatment will be evaluated according to IMWG uniform response criteria ([Appendix 5](#)) ([68, 69](#)).

Evaluations will occur once during the Screening Period (Days -28 and -1), 8 weeks after starting vemurafenib, every 28 days thereafter during the Treatment Period, and at the End of Treatment Visit.

Serum M-protein level will be quantitated using densitometry on serum protein electrophoresis (SPEP) by immunofixation.

Urine M-protein measurement will be estimated using 24-hour urine protein electrophoresis (UPEP) only. Random or 24-hour urine tests measuring kappa and lambda light chain levels are not reliable and are not recommended. For oligosecretory and light chain myeloma patients, serum free light chains will be measured.

Patients will need to have two consecutive assessments of CR, sCR, VGPR or PR to be considered a responder.

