For patients with MM, responders will be defined as patients with CR, sCR, PR and VGPR status. All other definitions for secondary endpoints for these patients will be similar to definitions above.

The best (confirmed) overall response (BOR) will be also assessed at the end of Stage II for each cohort. BOR is defined as the best response recorded from the first day of study treatment until disease progression/recurrence or death. To be assigned a status of PR or CR (i.e., a responder), changes in tumour measurements must be confirmed by repeat assessments that should be performed no less than 4 weeks after the criteria for response are first met, i.e., patients need to have two consecutive assessments of PR or CR to be a responder. Only patients with measurable disease at baseline will be included in the analysis of the BOR. Patients without a post-baseline tumour assessment will be considered to be non-responders. Duration of confirmed response is defined as the period from the date of initial PR or CR that contributed for the BOR status until the date of progressive disease or death from any cause. Patients with no documented progression after CR or PR will be censored at the last date at which they are known to have had the CR or PR, respectively. The method for handling censoring is the same as described for the PFS.

For responders in BOR, time to response is defined as the time from the first day of study treatment to the date of first CR or PR. The censoring rules will be similar to those of the PFS.

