8.3 STATISTICAL AND ANALYTICAL METHODS

8.3.1 Statistical Model

The main analysis for RR will use an adaptive design based on Simon's two stage design for a single proportion (70).

Stage I will be defined as when a pre-specified number of patients (as determined in the Sample Size section) will have a minimum of 8 weeks of treatment, develop progressive disease, prematurely withdraw from the study medication, or die, whichever occurs first.

If a pre-specified minimal RR will not be achieved in certain cohorts in the first stage of the study in certain cohorts, this cohort will be closed and no further enrolment of patients will be performed for that cohort. However, if a clear clinical benefit has been observed for patients in the cohort, e.g. majority of patients recorded SD at Week 8 and no CR or PR is recorded, then enrolment into Stage II might be allowed for this cohort after discussion with the Sponsor and study Steering Committee. Otherwise, enrolment will continue into Stage II until a pre-determined number of additional patients has been reached (as explained in the Sample Size section). At the conclusion of this study, vemurafenib will be declared effective or ineffective for each indication (cohort) based on rules for Stage II.

The analysis at Stage II (for lower or higher desirable response) for each cohort will be performed when all patients enrolled in the study, as estimated in the Sample Size section, will have a minimum of 8 weeks of treatment, develop progressive disease, withdraw, or are lost to follow-up, whichever occurs first.

Recruitment into any cohort/indication can be expanded up to a total of 70 patients if a response rate has been demonstrated in Stage II of that cohort as per stopping rules defined in the protocol or a clear clinical benefit for patients is observed. This will be decided by the Sponsor in discussion with study Steering Committee.

In case a cohort/indication is expanded to up to 70 patients, the primary analysis for efficacy will occur once all patients have been followed up for 9 months after last patient had been enrolled in that cohort, or the patient develops progressive disease, withdraws consent, or is lost to follow-up, whichever occurs first.

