8.3.1.2 Stopping Rules for Enrolment and Screening

If no patients are enrolled in the remaining cohorts one year after any of the cohorts has completed enrolment, then enrolment in those remaining cohorts will be stopped (patients already in screening will be allowed to enrol if eligible).

Individual cohorts may temporarily stop enrolment to allow for the stage I analysis before progressing to stage II.

Individual cohorts may temporarily stop screening to allow for the stage I analysis before progressing to stage II.

The decision to carry on enrolment of CRC patients into Cohort 3a (vemurafenib monotherapy) and/or enrol patients into Cohort 3b (combination of vemurafenib and cetuximab) will be based on the stage I analysis for Cohort 3a (vemurafenib monotherapy). This will be decided by the Sponsor in discussion with study Steering Committee.

The decision to continue enrolment in Cohort 3b after the Part I dose escalation phase will be decided by the Sponsor in discussion with study Steering Committee.

1. Rules for Stage I

Stage I will be stopped if the number of responders (unconfirmed) is less than the pre-specified number in the [Table 15](#) (e.g. if there is none or only one responder out of first seven patients). However if a clear clinical benefit has been observed for patients in the cohort, e.g. majority of patients recorded SD at Week 8 and no CR or PR is recorded, then enrolment into Stage II might be allowed for this cohort.

If there is the required response during Stage I or a good clinical benefit is observed for particular cohort as mentioned above, then additional patients will be enrolled in the second stage of the corresponding cohort, in order to achieve total number of patients as specified in the [Table 15](#) and [Table 16](#) below (Sample Size estimation section).

Cohort 7 will be closed to enrolment when all other cohorts are closed and results are reported, regardless of the number of patients recruited at that time. This cohort may be quite heterogeneous and will be examined primarily to seek efficacy signals in the relatively rare BRAF V600 mutation-positive tumours.

2. Rules for Stage II

A study treatment will be considered to be efficacious in a cohort in Stage II if

- there is no unacceptable toxicity and
- the number of responders is equal or above the specified number in the sample size calculations, as presented in [Table 16](#) or
- best overall response, BOR (confirmed) is higher than 15%.

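### The protocol defines the primary Week 8 response both with and without confirmation, and tests confirmed best overall response at a Stage II cut-off too early for late enrolees to be confirmed

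*Protocol*

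**What the plan says.** **No confirmation required.** Section 8.1.1 states that for solid tumours "responders at Week 8 will be defined based on tumour assessment status of PR or CR at Week 8"; the synopsis paragraph on the primary variable says the same. For Stage I, Section 8.3.1.2 states "Stage I will be stopped if the number of responders (unconfirmed) is less than the pre-specified number". Section 8.1.2 labels the duration of response of Week 8 responders as unconfirmed.

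**Confirmation required.** The synopsis efficacy section says "The primary endpoint will be RR at Week 8 in each indication", and its next sentence requires a solid-tumour responder to be confirmed at least 4 weeks later. Section 5.3.6.1 repeats this: "patients need to have two consecutive assessments of PR or CR to be a responder". Section 5.3.6.2 says of myeloma: "Patients will need to have two consecutive assessments of CR, sCR, VGPR or PR to be considered a responder". Footnote 2 to the IMWG table in Appendix 5 applies the two-assessment requirement to every response category.

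**Stage II.** The synopsis says "The analysis at Stage II (for lower or higher desirable confirmed response) for each cohort will be performed"; Section 8.3.1 says "The analysis at Stage II (for lower or higher desirable response) for each cohort will be performed". Both set the analysis at a minimum of 8 weeks of treatment per patient, or earlier progression, withdrawal or loss to follow-up. Under Section 8.3.1.2 a cohort succeeds, absent unacceptable toxicity, if it reaches the tabulated responder count (5 of 19 or 6 of 13) or if confirmed BOR exceeds 15%. Section 8.1.2 adds: "The best (confirmed) overall response (BOR) will be also assessed at the end of Stage II for each cohort".

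**Schedule.** Solid tumours are imaged every 8 weeks (Section 5.3.6.1). Myeloma is assessed at Week 8 and every 28 days thereafter (Section 5.3.6.2).

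**The concern.** Two things are at stake.

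First, the primary endpoint has two definitions in current text. The tabulated counts help decide whether a cohort is declared effective and whether it may expand to as many as 70 patients, so what counts as a response should not depend on which section the analyst opens. Myeloma is the sharpest case. Section 8.1.1 applies IMWG criteria at Week 8, the protocol's own IMWG footnote requires two consecutive assessments, and Week 8 is the first assessment after baseline. Read literally, no myeloma patient could be a responder at Week 8.

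Second, a criterion that needs two assessments is read at a cut-off that guarantees only one. A late-enrolled responder would count as not confirmed because of timing, not because the response failed to hold.

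**Working it through.** **Step 1. Reproduce the stated design.** Inputs (Sections 8.3.1.1 and 8.4): undesirable rate 15%, desirable rates 35% and 45%. With 2–4 responders among 7, enrol to 19 and require at least 5. With 5 or more among 7, enrol to 13 and require at least 6. With one binary response per patient at rate p,

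P(success) = Σ(x=2..4) b(x; 7, p)·P[Bin(12, p) ≥ 5−x] + Σ(x=5..7) b(x; 7, p)·P[Bin(6, p) ≥ 6−x].

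- p = 15%: 0.0990 + 0.0008 = 0.0998
- p = 35%: 0.6532 + 0.0521 = 0.7053
- p = 45%: 0.7330 + 0.1497 = 0.8827

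This fits the stated 10% and 70%, and meets the stated 80% as a minimum.

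**Step 2. Timing.**

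| | First post-baseline assessment | Next assessment | Guaranteed at the Stage II cut-off |
|---|---|---|---|
| Solid tumours | Week 8 | Week 16 | Week 8 only |
| Myeloma | Week 8 | Week 12 | Week 8 only |

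Eight weeks is a minimum, so earlier enrolees may already have a second assessment. The affected group is responders with less than about 16 weeks of follow-up (12 in myeloma).

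**Step 3. Confirmation ratios, for illustration.** The protocol reports confirmed and unconfirmed rates only for melanoma: 56.3/81.3 = 0.69 in the phase I extension cohort and 57/69 = 0.83 in BRIM-2 (investigator assessment).

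**Step 4. The BOR limb.** 0.15 × 19 = 2.85, so 3 of 19 suffices; 0.15 × 13 = 1.95, so 2 of 13 suffices. Any cohort with 5 of 19 or 6 of 13 confirmed responders has therefore already met the BOR limb. If the table count is confirmed, the BOR limb alone decides.

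**Step 5. Full Stage II rule, everyone confirmable.** Assumptions: p is the Week 8 unconfirmed rate; Stage I uses unconfirmed counts; each Week 8 response is confirmed independently with probability c; responses first seen after Week 8 and the toxicity condition are ignored. Success means table count reached OR confirmed BOR above 15%.

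| p | c | Table count unconfirmed | Table count confirmed | Difference (points) |
|---|---|---|---|---|
| 35% | 0.83 | 75.3% | 74.7% | 0.6 |
| 35% | 0.69 | 74.0% | 70.6% | 3.4 |
| 45% | 0.83 | 89.5% | 89.3% | 0.2 |
| 45% | 0.69 | 89.3% | 87.4% | 1.9 |

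**Step 6. Immature confirmation.** Further assumption: the last six patients enrolled have only a Week 8 scan, so none of them can be confirmed. At p = 35%, success is about 73–74% if the table count is unconfirmed and 57–67% if it is confirmed. The ranges cover c = 0.69 to 0.83.

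**The case against.** The strongest reply is that Section 8, the statistical section, is consistent on its own. Week 8 response is status at Week 8, Stage I is labelled unconfirmed, and the two-assessment requirement is attached to BOR. Sections 5.3.6.1 and 5.3.6.2 are general response criteria that mention neither the Week 8 rate nor the stage rules. That is a fair account of the likely intent, and the fix adopts it. It does not remove the conflict: those sections say without qualification who is a responder, the synopsis puts the confirmation sentence directly after the Week 8 endpoint, and its Stage II sentence carries the word *confirmed*.

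A reader might infer a large loss of power. Counting confirmed responses against 5 of 19 and 6 of 13 alone gives 42–57% at a true 35% (against 70.5%) and 64–79% at 45% (against 88%). The arithmetic is right, but the documents do not support it as the power of the rule, because the written rule also accepts confirmed BOR above 15%. With that limb included, most of the loss disappears (Step 5).

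A reader might also infer that nobody can be confirmed when Stage II is analysed. That goes too far, because 8 weeks is a minimum and early enrolees will often have a second assessment. The interim analysis section lists a Week 16 look, but does not tie it to the Stage II trigger, so it does not solve the problem for late enrolees.

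**Conclusion.** The contradiction in the primary endpoint is real and in current text, and for myeloma the literal reading is unworkable. The timing mismatch for confirmed BOR is also real, but limited to late enrolees, for whom it biases BOR downward.

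The size is modest with mature confirmation: about 0.2 to 3.4 percentage points in the chance of declaring success. It grows when the two problems combine. At a true 35% rate, with confirmed counts and six patients not yet confirmable, success falls to 57–67%, against about 73–74% with unconfirmed counts. These figures rest on melanoma confirmation ratios, which may not carry over to other tumour types, on independent confirmation, and on an assumed number of late enrolees. They show scale only. The point should be fixed; it does not undermine the design.

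**What to change.** 1. In the synopsis efficacy section and Sections 5.3.6.1, 5.3.6.2 and 8.1.1, state that the primary endpoint and the Stage I and Stage II table counts use investigator-assessed status at Week 8 without confirmation. For myeloma, add that this holds notwithstanding the two-assessment footnote in Appendix 5.
2. Limit the two-consecutive-assessments requirement to BOR/ORR and confirmed duration of response.
3. Delete the word *confirmed* from the synopsis sentence on the Stage II analysis, so that it matches Section 8.3.1.
4. Assess the confirmed-BOR criterion only once every Stage II patient has had the confirming assessment (Week 16 for solid tumours, Week 12 for myeloma) or has progressed, withdrawn or died.

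Items 1 to 3 are wording. Item 4 delays the BOR read-out by about 8 weeks in solid tumours (16 − 8) and 4 weeks in myeloma (12 − 8). The Week 8 table count can still be read on the existing timetable, and no sample size, visit or treatment changes.
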